1.0 Objectives

1.1 Study Objectives

To study the effectiveness of Spheno-Palatine (SP) ganglion block to alleviate the pain of post-dural puncture headache (PDPH).

1.2 Primary Study Endpoints

1. To study the effectiveness of SP ganglion block in relieving post-dural puncture headache in terms of
 - a. Number of subjects who get relief of pain
 - b. The onset time to pain relief after application of block
 - c. The duration of pain relief
 - d. The incidence of recurrence of post-dural puncture headache

1.3 Secondary Study Endpoints

1. To monitor any complications due to SP ganglion block
2. To measure patient satisfaction
3. To monitor any residual effects at 1 months after the SP block

2.0 Background

2.1 Scientific Background and Gaps

Lumbar puncture is a commonly performed diagnostic procedure in medicine and also for anesthesia. Inadvertent dural puncture can occur during epidural anesthesia and placement of an epidural catheter. Headache after a dural puncture is not uncommon and is excruciatingly painful. Most often it is self-limited and the pain subsides within 1-2 weeks. However, if left untreated, it can lead to considerable morbidity including chronic neck and back pain, subdural hematoma, seizures and even death.

According to the Headache Classification Committee of the International Headache Society, headache after lumbar puncture is defined as “bilateral headaches that develop within 7 days after a lumbar puncture and disappears within 14 days. The headache worsens within 15 min of resuming the upright position, disappears or improves within 30 min of resuming the recumbent position”. This definition helps to avoid confusion with migraine or simple headache after lumbar puncture.

Currently, the standard practice to manage this headache is to do an epidural ‘blood-patch’, wherein an anesthesiologist performs an epidural puncture in the lumbar spine after numbing the skin and subcutaneous tissue with 2-3 ml of 2% lidocaine and injects 20-30ml of the patient’s blood into the epidural space. The intention is for the blood to clot and seal the dural puncture. This is effective about 90% of the time and can be repeated if it fails. Introduction of infection, arachnoiditis, or another inadvertent dural puncture are possible complications. Some patients opt not to have the epidural blood patch for fear of another inadvertent dural puncture and choose the conservative management.

The other forms of therapy are strict bed rest for up to 7 days, hydration, caffeine, and epidural saline infusion. There are case reports of managing PDPH with administration of ACTH. There are a few case reports about use of SP ganglion block for PDPH but no prospective studies looking at onset, duration, side effects and long term follow up after Sphenopalatine ganglion block.

2.2 Previous Data

Here at HMC, we have performed the SP ganglion block in two patients who could not be offered epidural blood patch because they were on anti-coagulants. The block was effective and both were back to normal activities of daily living within 24h.

2.3 Study Rationale

According to the Monro-Kellie hypothesis, within the confines of the cranium, the volume of CSF, blood and brain matter is kept in harmony. Changes in volume of any one will cause compensatory changes in one or both of the other.

A dural puncture causes loss of CSF and this is compensated for by an increase in cerebral blood flow (CBF) by vasodilatation, which in turn causes headache. This vasodilatation is mediated by parasympathetic inputs that synapse in the Sphenopalatine ganglion. Blockade of this ganglion would reduce parasympathetic activity and mitigate the headache.

SP ganglion block has been used to treat migraine and cluster headaches.

3.0 Inclusion and Exclusion Criteria

3.1 Inclusion Criteria

1. Age greater than or equal to 18 years
2. Complains of symptoms suggestive of post-dural puncture headache
3. Has a history of dural puncture (lumbar puncture or accidental dural puncture during epidural placement) within the previous 7 days
4. Sex: male or female (including nursing females)
5. Fluent in written and spoken English

3.2 Exclusion Criteria

The following groups of patients will be excluded

1. Those with a known history of hypersensitivity to local anesthetics of the amide type or to other components of GLYDO
2. Those with any congenital or acquired, anatomical deformity of the nostril, which preclude performing the block
3. Pregnant woman
4. Tumors of the nasal cavity, sinuses, and nasopharynx
5. Hypertension
6. Hereditary hemorrhagic telangiectasia
7. Use of anticoagulants such as clopidogrel, or warfarin
8. Clotting factor (e.g. Von Willabrand's disease (most common), Factor VIII deficiency (Hemophilia A), Factor IX deficiency (Hemophilia B), and Factor XI deficiency)
9. History of epistaxis within the prior 30 days
10. Those who refuse to consent to participate in the study
11. Patients who have had a failed epidural blood patch
12. Cognitive Impairment
13. Prisoner

3.3 Early Withdrawal of Subjects

3.3.1 Criteria for removal from study

If a patient consents to participate but cannot tolerate the procedure of SP block, then they will be removed from the study

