3.3.2 Follow-up for withdrawn subjects

If the subject is withdrawn from the study, they will be offered other forms of therapy and followed up, if they allow.

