7.3 Duration of Participation

The patients will be contacted on post –procedure Day 1, 2 and 7. During the phone call, they would be asked about their original complaints (headache, neck spasm), and if they have any new symptoms or discomforts.

The participants will be contacted by phone about 1 month after the procedure to ask if they have any residual neck or back pain or any other side effect. They will also be asked if they are satisfied with their management of PDPH

The follow-up phone calls will be made even if the SPG block fails and the subject opts for either an epidural blood patch or conservative management.

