8.2 Sample size determination

Convenience Sample: This is a pilot study and this number was selected to complete this study over one year. The data collected will be used for a formal sample size calculation, if appropriate, to plan a larger study.

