8.3 Statistical methods

It would be mainly descriptive statistics looking at time to onset of pain relief, the duration of pain relief, failure of the procedure to relieve PDPH, description and frequency of any side effects at one week and 1 month.

The number of patients who do not get any or inadequate pain relief and if they need an epidural blood patch, it will be considered a failure of this technique.

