10.0 Data and Safety Monitoring Plan

10.1 Periodic evaluation of data

Every patient will be reviewed for any harmful effects due to the SP ganglion block

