10.3 Method of collection of safety information

Safety information will be collected by interview of subjects at the time of intervention. Afterwards, safety information will be collected by telephone interview.

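### Subjects who cannot tolerate the block are removed from the study, and the plan does not say whether they count in the relief result

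*Combined protocol and SAP*

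**What the plan says.** All references are to the combined protocol and SAP.

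- **Removal.** Section 3.3.1 gives the only removal criterion: "If a patient consents to participate but cannot tolerate the procedure of SP block, then they will be removed from the study".
- **After removal.** Under section 3.3.2, "they will be offered other forms of therapy and followed up, if they allow". Nothing is said about analysis.
- **Block failure.** Section 7.3 treats the other unsuccessful outcome differently: "The follow-up phone calls will be made even if the SPG block fails".
- **Endpoint.** The first primary endpoint in section 1.2 is "Number of subjects who get relief of pain", a count without a denominator. Section 8.1 sets the number of subjects at thirty and does not say thirty of what.
- **Analysis.** Sections 8.3 and 10.7 plan descriptive statistics that include "failure of the procedure to relieve PDPH". Section 8.3 adds a definition of failure that joins absent or inadequate relief to the need for an epidural blood patch. Neither section mentions removed subjects.
- **Safety.** Section 10.1 states: "Every patient will be reviewed for any harmful effects due to the SP ganglion block". Section 10.3 states: "Safety information will be collected by interview of subjects at the time of intervention". Section 19.2 also provides for adverse event questions during the procedure.
- **Later use.** Section 8.2 states: "The data collected will be used for a formal sample size calculation, if appropriate, to plan a larger study".

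**The concern.** Failing to tolerate the block is not an eligibility failure. It happens after consent, because of the intervention, and it is one of the ways in which the treatment can fail to help. Taking such subjects out while keeping those whose completed block did not work treats two unsuccessful outcomes differently, and the difference favours the block.

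The study is a single-arm, open-label pilot, so its descriptive results are its main product. Two analysts with the same data could report different relief rates, depending on how each reads removal. The higher figure could then be carried into the planning of a larger study as if it applied to everyone in whom the block is tried.

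**Working it through.** **There is no planned figure to reproduce.** Thirty is a convenience number chosen to fit one year (section 8.2). The documents give no relief rate, intolerance rate, power or dropout allowance.

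**Does any section return removed subjects to the efficacy summary?**

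1. Section 3.3.2 covers other therapy and follow-up by agreement, not analysis.
2. Section 7.3 continues the calls after a failed block and does not mention intolerance.
3. The failure definition in section 8.3 would fit an intolerant subject without relief who goes on to a blood patch. Taken at its word, it misses one who chooses conservative care, an option offered in sections 5.1.1.2 and 7.2.1.
4. Sections 1.2, 8.1 and 10.7 give no denominator and no analysis set.

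So no section does.

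**Size of the effect.** Inputs, all assumed except the 30: the block is attempted in 30 subjects, k are intolerant and counted as not relieved, and x are relieved.

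- Rate among tolerators: x/(30−k)
- Rate among all attempted: x/30
- Ratio: 30/(30−k)

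Intervals are exact (Clopper-Pearson) 95%.

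| k | Ratio | Tolerators | All attempted | Shift |
|---|---|---|---|---|
| 0 | 30/30 = 1.000 | same | same | 0 |
| 1 | 30/29 = 1.034 | 20/29 = 69.0% (49.2 to 84.7) | 20/30 = 66.7% (47.2 to 82.7) | 2.3 points |
| 3 | 30/27 = 1.111 | 19/27 = 70.4% (49.8 to 86.2) | 19/30 = 63.3% (43.9 to 80.1) | 7.0 points |

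The intervals are 35.5 to 36.4 points wide, so the shift is well inside sampling error at either count.

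**Does the direction depend on the counting rule?** Let r of the k intolerant subjects be relieved by a partial block. The rate among all attempted becomes (x+r)/30, and the tolerator rate is higher only if r/k is below x/(30−k). With k=3 and x=19 (tolerator rate 70.4%):

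- r=1: 20/30 = 66.7%, so the tolerator rate is 3.7 points too high.
- r=2: 21/30 = 70.0%, 0.4 points too high.
- r=3: 22/30 = 73.3%, about 3 points too low.

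The overstatement therefore holds as long as intolerant subjects are relieved less often than those who complete the block.

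**Related count.** Section 19.7 bases its stopping rule on the opening five subjects, while section 10.6 times data review by patients who have received the intervention. Neither says whether a removed subject counts.

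**The case against.** The strongest reply is that the plan never states a biased analysis. The endpoint is a count, and if intolerant subjects are taken as not relieved, the count is the same whether or not they are included. Section 3.3 concerns withdrawal from participation, and withdrawn subjects may still be followed, so removal need not mean that their data are dropped. This stands as far as it goes: the tolerator-only rate is an inference. It does not settle the matter, because a count becomes interpretable only over a denominator, and the plan gives none.

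Second, every count above is assumed. Section 11.0 lists mostly brief or mild effects of the swab, and section 3.2 excludes obstructive nasal deformity, nasal tumours and recent nosebleeds. None or one intolerant subject is plausible, which means a shift of 0 to 2.3 points. That is fair, and it is why the point is minor. Against it, the protocol itself foresaw intolerance by writing a rule for it.

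Third, a reader might infer more than the documents support:

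- *That harms in intolerant subjects are lost.* Sections 3.3.2, 10.1, 10.3 and 19.2 provide for safety information on them.
- *That only the relief count is affected.* A subject relieved after a partial block would also have onset, duration and recurrence to report, and satisfaction at 1 month also depends on who is included.
- *That sections 10.6 and 19.7 contradict each other.* One sets the timing of review and the other is a stopping rule. Their wording differs and leaves a question open, but the two are not in conflict.

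**Conclusion.** The point holds as a gap created by a stated rule. Section 3.3.1 takes subjects out for an event that the block causes, and nothing says whether they enter the efficacy summary. Exclusion from the analysis is the natural reading but not the only one, and the documents do not support saying that the plan prescribes a relief rate among tolerators.

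If that reading is applied, the overstatement is the factor 30/(30−k): none at k=0, 2.3 points at k=1 and 7.0 points at k=3 in the examples. This rests on assumed counts, on 30 meaning subjects attempted, and on intolerant subjects counting as not relieved. No test or threshold is attached to the rate, and its use in planning a larger study is conditional. Severity is minor.

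**What to change.** **Section 3.3.1.** Reword it so that intolerance ends the procedure but the subject stays in the analysis, with follow-up by agreement as in section 3.3.2 and clinical management unchanged.

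**Section 8.3, matched in section 10.7.** State that:

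1. the first primary endpoint is reported over all subjects in whom the block was attempted, with thirty in section 8.1 defined to match;
2. non-completion counts as not relieved in the main summary, and this is reconciled with the existing failure definition, including for subjects who choose conservative care;
3. the completers-only rate, and any relief after a partial block with its onset, duration and recurrence, are supportive results;
4. the number intolerant is reported, with reasons.

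**Sections 10.6 and 19.7.** Reconcile them on whether a removed subject counts. That answer is for the investigators and is not proposed here.

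**Cost.** Mainly wording. The data sheet is not among the documents, so one or two added items (reason for stopping, relief after a partial block) may be needed. The reported rate may be slightly less favourable, and it may slightly understate relief if a partly blocked subject improves. The supportive results would show that.

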3.3.2 Follow-up for withdrawn subjects

If the subject is withdrawn from the study, they will be offered other forms of therapy and followed up, if they allow.

4.0 Recruitment Methods

4.1 Identification of subjects

Patients who develop PDPH, both in-patients and those who arrive in the Emergency Department (ED) are referred to the Anesthesiologists-on-call, for management. A system will be set in place to inform one of the investigators when such a patient is referred. If suitable, one of the investigators will consent the patient and perform the block.

4.2 Recruitment process

When informed, one of the investigators will approach the patient and explain the study and if they are willing will consent them and perform the block.

4.3 Recruitment materials

None.

4.4 Eligibility/screening of subjects

Not applicable

5.0 Consent Process and Documentation

5.1 Consent Process

5.1.1 Obtaining Informed Consent

5.1.1.1 Timing and Location of Consent

When identified as a potential candidate for the study in the ward or in the ED by one of the physician investigators. The consent will be reviewed with the patient by one of the physician investigators. The consent will be signed at that time if the subject is willing to participate in the research.

5.1.1.2 Coercion or Undue Influence during Consent

Patients that are enrolling in the study will be told that participation is voluntary and will not in any way compromise the standard of care that they will receive.

Physician investigators will explain that the current standard treatment is bed rest, hydration and analgesics or an epidural blood patch. They will be free to choose any of the options.

5.1.2 Waiver or alteration of the informed consent requirement

A waiver of consent is requested to review medical record information to determine preliminary eligibility to participate in the research.

5.2 Consent Documentation

5.2.1 Written Documentation of Consent

The consent process will be documented in writing with the long form of consent documentation:

- The current IRB approved consent form will be obtained.
- We will verify that we are using the most current IRB-approved version of the study specific consent form and that the consent form is in language understandable to the subject.
- A copy of the consent form will be provided to the subject.

5.2.2 Waiver of Documentation of Consent (Implied consent, Verbal consent, etc.)

Not applicable

5.3 Consent – Other Considerations

5.3.1 Non-English Speaking Subjects

Not applicable

5.3.2 Cognitively Impaired Adults

5.3.2.1 Capability of Providing Consent

Not applicable

5.3.2.2 Adults Unable To Consent

Not applicable

5.3.2.3 Assent of Adults Unable to Consent

Not applicable

5.3.3 Subjects who are not yet adults (infants, children, teenagers)

5.3.3.1 Parental Permission

Not applicable

5.3.3.2 Assent of subjects who are not yet adults

Not applicable

6.0 HIPAA Research Authorization and/or Waiver or Alteration of Authorization

6.1 Authorization and/or Waiver or Alteration of Authorization for the Uses and Disclosures of PHI

Check all that apply:

- Not applicable, no identifiable protected health information (PHI) is accessed, used or disclosed in this study. [Mark all parts of sections 6.2 and 6.3 as not applicable]
- Authorization will be obtained and documented as part of the consent process. [If this is the only box checked, mark sections 6.2 and 6.3 as not applicable]
- Partial waiver is requested for recruitment purposes only (Check this box if patients' medical records will be accessed to determine eligibility before consent/authorization has been obtained). [Complete all parts of sections 6.2 and 6.3]
- Full waiver is requested for entire research study (e.g., medical record review studies). [Complete all parts of sections 6.2 and 6.3]
- Alteration is requested to waive requirement for written documentation of authorization (verbal authorization will be obtained). [Complete all parts of sections 6.2 and 6.3]

6.2 Waiver or Alteration of Authorization for the Uses and Disclosures of PHI

Not Applicable

6.2.1 Access, use or disclosure of PHI representing no more than a minimal risk to the privacy of the individual

6.2.1.1 Plan to protect PHI from improper use or disclosure

Information is included in the Research Data Plan Form.

6.2.1.2 Plan to destroy identifiers or a justification for retaining identifiers

Study information will be destroyed after the research has ended and all institutional/regulatory requirements for data retention have been met

6.2.2 Explanation for why the research could not practically be conducted without access to and use of PHI

Information must be obtained from the subject's electronic medical record during recruitment to determine eligibility and, in some cases, to confirm information discussed with the subject in regards to their medical history

6.2.3 Explanation for why the research could not practically be conducted without the waiver or alteration of authorization

The waiver is requested only for recruitment to determine subject eligibility to ensure that no medical conditions that fall into the exclusion criteria are present and would thus preclude enrollment. This waiver will minimize the enrollment of subjects' who may ultimately fail to meet the study inclusion/exclusion criteria.

6.3 Waiver or alteration of authorization statements of agreement

Protected health information obtained as part of this research will not be reused or disclosed to any other person or entity, except as required by law, for authorized oversight of the research study, or for other permitted uses and disclosures according to federal regulations.

The research team will collect only information essential to the study and in accord with the 'Minimum Necessary' standard (information reasonably necessary to accomplish the objectives of the research) per federal regulations.

Access to the information will be limited, to the greatest extent possible, within the research team. All disclosures or releases of identifiable information granted under this waiver will be accounted for and documented.

7.0 Study Design and Procedures

7.1 Study Design

Open-labelled, single arm, pilot study

7.2 Study Procedures

7.2.1 Study Intervention:

A urine pregnancy test will be done for all non-post-partum women.

Once the patient consents to participate in the study the following will be done.

- The worst pain score (on a scale 0-10) that the patient experiences while sitting at the edge of the bed for 5 minutes, will be recorded.
- An IV catheter will be placed and an infusion of IV fluid will be started, if the patient does not have already.
- Continuous ECG, pulse-oximeter and non-invasive blood pressure monitoring will be established and a skin temperature will be recorded.
- The patient will be placed in the supine position with the neck slightly extended.

Sphenopalatine block

Anatomy: The Sphenopalatine or the Pterygopalatine ganglion is a small (5 mm), parasympathetic ganglion located in the pterygopalatine fossa, posterior to the middle nasal turbinate. It is separated by a thin layer of connective tissue and mucosa from the nasal cavity.

Lidocaine (2%) Swab Preparation:

Use of cotton-tipped plastic applicator with 2% Lidocaine jelly applied (see section 7.4.6.3): One 2% lidocaine treated cotton-tipped applicator will be gently inserted into each nostril, along the floor of the nose. Slight rotatory motion of the applicator will be used to insert it as far as it goes with the intention to reach the nasopharyngeal wall (posterior wall of the nose). At that position the applicator will be left undisturbed for 5 minutes. The swabs will be taken out and this will be repeated twice more, using fresh 2% lidocaine treated swabs. The whole procedure will take about 30 minutes.

After the procedure the patient will be asked for any side effects and if they are comfortable will be asked to sit up with their legs dangling over the side of the bed. If they can sit for about 15

minutes without pain and are hemodynamically stable, they will be asked to stand and walk. At any stage the headache returns or they cannot sit up or stand for any other reason, they will be made to lie down.

If the headache resolves, they will be discharged to go home, if acceptable by the primary physician. The patient will be encouraged to drink plenty of fluids and caffeinated drinks and get as much bed rest as possible for the next 3 days.

After the patient has given informed consent, 2% Lidocaine jelly (Glydo) obtained from pharmacy supply, just like any other standard of care medication and will be administrated and documented as any other standard of care medication. Post research intervention, a study team member will securely email [name], Senior Representative Patient Accounts, at [contact] within 24-48 hours with identifiers (MRN, FIN, and Date of Service). She will manually pull the charge from the patient's bill and direct the research charge to the Sponsor, in this case the Department of Anesthesiology and Perioperative Medicine.

On Day 1, 2, and 7 after the procedure, one of the investigators will call them to ask a set of questions about the headache and any side effects. A follow up phone call, at 1 month after the SP ganglion block, will be made to ask for any residual headache or other symptoms and their satisfaction with the management. (Data Sheet)

If the headache does not get relieved, the patient will have the option to undergo an epidural blood patch or opt for a conservative management of bed rest, analgesics and oral fluids. These options will also be available if the headache were to recur after the patient goes home.

We will also collect information (demographic details, past medical history, details of the procedure that led to the current headache) from the patient's medical record for this research.

7.2.2 Post-treatment Days 1, 2, 7

Patients will be followed up by either a visit, if the patient is an in-patient, or by phone if the patient is at home.

Questionnaire – pain relief, residual pain (intensity and location), side effects, nasal bleeding (See Data Sheet in supporting materials)

7.2.3 1 month Post-treatment

A follow up phone call at 1 month after the SP block will be made to ask for any residual headache or other symptoms and their satisfaction with the management.

